**Aims 3, 4, and 5 pertain to all 210 participants randomized (n=105 to receive BATA and n=105 to receive MBCT).**

Aim 3: We predict that BATA will produce clinically and statistically significant improvements in anhedonia and functional outcomes that exceed those due to the comparison treatment.

Aim 4: We predict that BATA will improve behavioral indices of reward sensitivity.

Aim 5: To evaluate the effects of BATA versus a comparison treatment on neural response to rewards. We predict that, consistent with Aim 1, BATA will increase right CN activation during reward anticipation and decrease rACC activation during reward outcomes and that BATA will not decrease amygdala activation to threat, confirming the specificity of BATA for targeting these positive valence neural systems. This Aim will provide a replication and extension of Aim 1 findings with a larger sample and with an optimal treatment dose.

In the PET sub-study, Hypothesis 1- BATA, but not the comparison treatment, will result in increased phasic striatal DA release but will not influence background DA striatal tone. Hypothesis 2- that normalization of fMRI-derived mesocorticolimbic activation due to BATA specifically will be associated with increased phasic DA release but no change in background DA tone during incentive processing.

This is not a pilot study but rather a Phase I/II study. The R61 phase (Phase I) of the protocol is designed to provide preliminary data for the acceptability, identification of the optimal dose of BATA as well as the preliminary efficacy of BATA in subjects with anhedonia compared to those in the MBCT control group. Using the fMRI data, this phase of the study will test if BATA produces changes in neural responses to reward anticipation and reward outcomes that exceed changes in the MBCT group and does not impact neural responses to threat. As such, a small group (N = 60) of subjects will be in this blinded phase and they will complete up to a total of 4 fMRI scans (pre-treatment, week 8, 12 and post-treatment). The R61 study will be entering a no-cost extension at the end of the current project period to allow for completion of data collection for this phase. Due to limited funds, the number of scans obtained is being reduced from up to 4 scans to two scans (pre- and post-treatment.) for participants

who are consented at UNC as of November 1. In the R33 phase (Phase II) of the study, a larger group (N=150) of subjects will complete the study having been randomized to either BATA or MBCT and undergone a pre-treatment and post-treatment fMRI. This second phase will continue to test the efficacy of BATA over MBCT on changing anhedonic symptoms and functional outcomes for all 210 subjects from both phases. The effects of BATA on behavioral indices of reward sensitivity and neural response to reward will also be evaluated. If this study, across both phases, shows that BATA, relative to MBCT, engages brain targets in hypothesized ways and decreases anhedonia, future research with larger samples will investigate the effectiveness and efficacy of this novel intervention. This study involves the evaluation of a novel behavioral treatment for anhedonia called Behavioral Activation Treatment for Anhedonia (BATA). It is a collaboration with the Duke Department of Psychiatry, and this protocol will be linked to a companion Duke's IRB protocol via a Data Transfer Agreement (DTA.)

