**Aims 3, 4, and 5 pertain to all 210 participants randomized (n=105 to receive BATA and n=105 to receive MBCT).**

**Aim 3:** To evaluate the effects of BATA versus an active comparison treatment on anhedonic symptoms and functional outcomes.

**Aim 4:** To evaluate the effects of BATA versus an active comparison treatment on behavioral indices of reward sensitivity.

**Aim 5:** To evaluate the effects of BATA versus a comparison treatment on neural response to rewards.

PET Aims specifically refer to the 30 subjects who consent to the optional PET sub-study:

**Aim 1 (PET):** To evaluate the effects of BATA, relative to a comparison treatment, on PET-derived measures of DA functioning during incentive processing. We hypothesize that BATA, but not the comparison treatment, will result in increased phasic striatal DA release but will not influence background DA striatal tone.

**Aim 2 (PET):** To evaluate relations between treatment-related changes in fMRI-derived mesocorticolimbic activation and PET-derived DA functioning in the BATA-treated group. We hypothesize that normalization of fMRI-derived mesocorticolimbic activation due to BATA specifically will be associated with increased phasic DA release but no change in background DA tone during incentive processing.

Exploratory Aims include the data from the EMA optional study: Passive location tracking (PLT) data during the period of EMA monitoring will be collected via the MetricWire app to allow us to compare distance traveled before and after both treatments as a secondary, exploratory measure of behavioral activation. Follow-up analyses will evaluate relations between motion tracking, behavioral, brain, and clinical measures of response to both treatments.

**Specific Aim 3 (EMA):** To evaluate if BATA, relative to a comparison treatment, produces improvements in real-world positive affect and the use of BATA skills. We hypothesize that BATA, but not the comparison treatment, will be associated with improvements in real-world positive affect and the use of BATA skills.

**Specific Aim 4 (EMA):** To evaluate relations between treatment-related changes in fMRI-derived mesocorticolimbic activation and real-world positive affect and the use of relevant BATA skills in the

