**Aims 1 and 2 pertain to the first 60 participants randomized (n=30 to receive BATA and n=30 to receive MBCT).**

Aim 1: We predict that BATA will increase right caudate nucleus (CN) activation during reward anticipation and decrease rostral anterior cingulate cortex (rACC) activation during reward outcomes, and that BATA will not decrease amygdala activation to threat, confirming the specificity of BATA to these positive valence neural systems.

Aim 2: We predict that the BATA group will show increased right CN activation during reward anticipation and decreased rACC activation during reward outcomes that will plateau after the optimal dose of the intervention has been delivered.

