### **Study Visits:**

Potential participants will complete the following:

- 1) A phone or online screen to determine initial eligibility via UNC's REDCap

- 2) A 1-2 clinical characterization visit(s) to determine eligible, and, if eligible, to characterize participants clinically. During COVID, can be split remote/in-person.
- 3) A pre-treatment 7 Tesla (7T) fMRI scan & if one of the first 60 subjects enrolled, have an initial blood draw of 10ml (2tsp). Update, the NARSAD blood protocol had entered an extension and has additional funds so up to 210 participants, in both phases, will have an initial blood draw of 10ml (2tsp). **As of 6/26/20, the blood protocol will no longer continue for any new participant enrolled in the study. As of the NCE 2022, this current amendment, imaging of new participants will end. Only enrollment into the therapy portion at Duke will continue.**
- 4) Patients will then be assigned randomly to the experimental treatment (BATA) or comparison treatment (Mindfulness Based Cognitive Therapy (MBCT)) for approximately 15 weeks of treatment.
- 5) The first 60 patients enrolled (n=30 who receive BATA and n=30 who receive MBCT) will additionally complete two additional, mid-treatment, fMRI scans as well as an additional blood draw at all other MRI visits. The 1st phase of the study entered the R61 no cost extension at the end of the project period & due to limited funds, participants will no longer be receiving up to 4 scans. Participants who consent at UNC on or after 11/1/18 will receive only pre- and post-treatment scans (2 scans total). **The R61 no cost extension has ended and the study has entered the larger R33 phase of the study and participants will continue to receive only pre and post treatment scans (2 total) and no bloodwork will be collected starting summer 2020 for new participants. \*\*No new enrollment to imaging at UNC will occur with the approval of the June 2022 NCE amendment.**
- 6) A post-treatment clinical characterization visit
- 7) A post-treatment 7T scan

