## 9.2 DATA ANALYSES & STATISTICAL CONSIDERATIONS

fMRI Analyses for Go/No-Go Decision for phase II (R33): Analyses of target engagement will focus on activation in the right CN during reward anticipation, the rACC during reward outcomes, and bilateral amygdala in response to threat. The decision to proceed to the R33 phase will rest on reward-related activation metrics from functional CN and rACC regions of interest (ROIs) derived from our preliminary studies (from [37]). We will make these functional ROIs publically available through the UNC BRIC's website for use by other researchers. Amygdala activation during the threat task will be evaluated using an amygdala ROI defined from the Harvard-Oxford subcortical structural probabilistic atlas. Data will be preprocessed using FSL (Oxford University, UK) as described in our work. We will ensure groups do not differ in head motion by calculating mean framewise displacement which yields, for each participant, a value indicating mean head displacement from one volume to the next. Hypotheses will be evaluated with a ROI approach whereby signal intensities are extracted from ROIs for the relevant task contrasts (i.e., potential win versus non-win trials during MID reward anticipation trials; wins versus non-wins during MID reward outcome trials; fearful and angry faces > shapes during the threat task). **Our go/no-go decision will be based solely on this ROI analysis.**

Exploratory Whole-brain Activation Analyses ROI analyses will be followed-up with whole-brain analyses that will yield activation maps thresholded at a False Discovery Rate of 0.01 to allow for an examination of activation in other reward processing regions, including the ventral striatum/nucleus accumbens, putamen, ventral tegmental area, and orbitofrontal cortex. To optimize BOLD signal coverage in the ventral tegmental area we will acquire high-resolution T1-weighted images with 1x1x1 mm voxel size to allow for precise registration and will use cardiac and respiratory gated imaging during the acquisition of structural scans to address pulsatile artifacts using retrospective corrections implemented with the FSL PNM toolbox.

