### 9.2.2 PLANNED INTERIM ANALYSES

*not-applicable*

*Only as R61 is ending to confirm approval of the R33 phase as noted above:* fMRI Analyses for Go/No-Go Decision for phase II (R33): Analyses of target engagement will focus on activation in the right CN during reward anticipation, the rACC during reward outcomes, and bilateral amygdala in response to threat. The decision to proceed to the R33 phase will rest on reward-related activation metrics from functional CN and rACC regions of interest (ROIs) derived from our preliminary studies (from [37]). We will make these functional ROIs publically available through the UNC BRIC's website for use by other researchers. Amygdala activation during the threat task will be evaluated using an amygdala ROI defined from the Harvard-Oxford subcortical structural probabilistic atlas. Data will be preprocessed using FSL (Oxford University, UK) as described in our work. We will ensure groups do not differ in head motion by calculating mean framewise displacement which yields, for each participant, a value indicating mean head displacement from one volume to the next. Hypotheses will be evaluated with a ROI approach whereby signal intensities are extracted from ROIs for the relevant task contrasts (i.e., potential win

versus non-win trials during MID reward anticipation trials; wins versus non-wins during MID reward outcome trials; fearful and angry faces > shapes during the threat task). **Our go/no-go decision will be based solely on this ROI analysis.)**

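### Aim 5 is called a replication of Aim 1, but its only planned test includes the Aim 1 participants whose ROI result decided whether R33 opened

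*Combined protocol and SAP*

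**What the plan says.** **Who is in each aim.** Section 4.1 states: "Aims 1 and 2 pertain to the first 60 participants randomized (n=30 to receive BATA and n=30 to receive MBCT"). For the later aims it states: "Aims 3, 4, and 5 pertain to all 210 participants randomized (n=105 to receive BATA and n=105 to receive MBCT"). The R33 phase adds the remainder: "a larger group (N=150) of subjects will complete the study". Since 60 + 150 = 210, every Aim 1 participant is also in the Aim 5 sample.

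**What Aim 5 claims.** It repeats the Aim 1 predictions for right CN, rACC and amygdala. Section 4.1 then describes it this way: "This Aim will provide a replication and extension of Aim 1 findings with a larger sample and with an optimal treatment dose".

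**The gate.** Section 9.2 says: "The decision to proceed to the R33 phase will rest on reward-related activation metrics from functional CN and rACC regions of interest (ROIs"), and adds: "Our go/no-go decision will be based solely on this ROI analysis". Section 9.2.2 places this look at the end of R61: "Only as R61 is ending to confirm approval of the R33 phase as noted above". No numeric criterion is given. Under Study Visits, Section 4.1 reports that the trial moved on: "The R61 no cost extension has ended and the study has entered the larger R33 phase of the study".

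**The model.** Section 9.2 gives a single treatment-by-region-by-time ANCOVA for Aims 1 and 5 together. It has no term for phase and makes no allowance for the gate, and no analysis is restricted to R33 participants.

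**The concern.** A replication asks whether a finding recurs in data that did not produce it. Here 60/210 = 28.6% of the planned Aim 5 sample did produce it. The other 150 participants are recruited only if the same regions of interest, in those same 60, looked favourable. If the R61 result was partly luck, that luck stays in the pooled estimate and makes a second significant result more likely than it would be in new participants.

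The phases also differ, and a model without a phase term cannot show it. Section 6.3 balanced R61 allocation within SHAPS groups of 20–30 and 31+, whereas R33 participants all score 30 or more. The sentence claiming replication also refers to an optimal dose. Section 6.1.1 says R33 duration stays at 8–15 weeks, and the R61 participants counted in Aim 5 were treated before any dose estimate existed. Those passages need to be reconciled.

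At stake is how the main mechanistic result is read: as two findings, or as one finding updated.

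**Working it through.** **Inputs from the documents**
- R61: 60 randomised, 25 per group expected complete. R33: 150. Total: 210 (Sections 4.1 and 9.1).
- fMRI alpha 0.025, sidedness not stated. Effect 0.75–1.25, metric not defined (Section 9.1).
- Retention from pre- to post-scan about 81% (Section 5.4).

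**Assumptions.** Gate form and cut-off, number of R33 participants imaged, one region at a time, equal arms.

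**1. The plan's own power figure.** Section 9.1 claims >90% for Aim 1; Aim 5 has no figure of its own. At effect 0.75 and two-sided 0.025:
- Read as a within-arm pre–post effect: noncentrality 0.75 × √25 = 3.75, power 90.5%. The claim is reproduced.
- Read as a between-group SD difference: 0.75 × √(25/2) = 2.65, power 63.3% (98.0% at 1.25).

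The claim therefore depends on the undefined metric, and so do steps 4 and 5.

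**2. Chance that the pooled test is significant after a passed gate, no true effect**

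Z_pooled = √(60/210) Z_R61 + √(150/210) Z_R33, so the correlation of Z_pooled with Z_R61 is √0.286 = 0.535. If the gate uses only within-BATA change, the correlation is 0.535/√2 = 0.378.

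P(Z_pooled > c | Z_gate > g) = Φ₂(−g, −c; ρ) / Φ(−g)

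| Gate (assumed) | g | c | ρ | Pooled | R33-only |
|---|---|---|---|---|---|
| Right direction, within BATA | 0 | 1.96 | 0.378 | 4.1% | 2.5% |
| Right direction, between groups | 0 | 1.96 | 0.535 | 4.6% | 2.5% |
| Significant, within BATA | 1.96 | 1.96 | 0.378 | 12.5% | 2.5% |
| Significant, between groups | 1.96 | 1.96 | 0.535 | 20.5% | 2.5% |
| Both at two-sided 0.025 | 2.24 | 2.24 | 0.535 | 16.0% | 1.25% |

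If R61 only just passed at z = 1.96, the new participants need z = (1.96 − 0.535 × 1.96)/√(1 − 0.286) = 1.08, not 1.96.

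If only 90, 60 or 30 R33 participants were imaged, the 20.5% becomes 27%, 34% or 46%.

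**3. Unconditional error.** The probability of passing the gate and then having a significant pooled test is 0.205 × 0.025 = 0.5%. A gate that can only stop the trial cannot raise the overall error of the pooled test.

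**4. Bias in the pooled estimate after a passed between-group gate.** With m = d√(25/2), the excess in R61 is √(2/25) × φ(g − m)/Φ(m − g). Its weight in the pooled estimate is 60/210.
- d = 0.75: R61 excess 0.118 SD (g = 1.96) to 0.157 SD (g = 2.24). Pooled excess 0.034–0.045 SD, or 4.5–6% of the effect.
- d = 1.0: about 1–1.5%. d = 1.25: under 0.3%.
- No true effect, g = 1.96, all 30 per arm contributing: expected R61 difference 2.338 × √(2/30) = 0.60 SD, adding 0.60 × 0.286 = 0.17 SD to the pooled estimate.

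**5. Power of an R33-only test.** Noncentral t, between-group effect 0.75, two-sided 0.025, noncentrality 0.75√(n/2):
- 61 per arm (0.81 × 75): 97%
- 40 per arm: 86%
- 30 per arm: 73%

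At an assumed effect of 0.5, 61 per arm gives 69%.

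**The case against.** The strongest reply is that nothing is hidden. Section 4.1 makes the statement under a heading that names all 210 participants, pairs replication with extension and a larger sample, and frames its conclusions across both phases. It never calls Aim 5 independent. That stands: a reader might infer that the trial promises independent confirmation, and the documents do not say so. But extension describes the pooled analysis, and no planned analysis corresponds to the other half of the claim.

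Second, the gate is undefined. Section 9.1 lists meeting pre-set target-engagement criteria separately from exceeding the comparison treatment, so the gate may be a within-BATA criterion rather than a between-group test. This stands, and it is why the size is a range that starts near 4%. The documents imply that the gate was passed, but they do not report the R61 result.

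Third, the pooled test is valid in the usual sense, and under the plan's own effects the bias is a few percent at most. Both points stand. They defend the pooled estimate as an estimate, but do not make it a replication.

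Fourth, an R33-only test could be weak. Section 4.1 ends imaging of new participants with the 2022 amendment and does not say how many had been imaged. This also stands, and is a reason to report the R33-only estimate with its interval rather than only a significance verdict.

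**Conclusion.** The point holds as one of labelling and a missing analysis. Followed as written, the plan would call a result a replication when it contains the data being replicated, selected on the same regions.

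Under no true effect, with 60 + 150 participants and the pooled test at z > 1.96, the chance of a significant pooled result after a passed gate is about 4–5% to 20.5%, depending on the gate, against 2.5% in new participants alone. With both thresholds at two-sided 0.025 and a between-group gate, it is 16.0% against 1.25%. The figures would be higher if fewer than 150 R33 participants were imaged.

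Two stronger readings are not supported. A reader might infer that the pooled test has an inflated type I error; it does not. A reader might also infer that a significant Aim 5 result is guaranteed; under no effect and the strictest gates shown, about 80% or more of pooled tests would still fail. If effects of 0.75–1.25 are real, read as between-group SD differences, the distortion of the pooled estimate is at most about 6%.

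**What to change.** In Sections 4.1 and 9.2:
- Add an analysis of the treatment-by-time effects in CN and rACC restricted to R33 participants, and use the word *replication* only for that result.
- Keep the pooled R61 + R33 analysis as the *extension* estimate, and add a phase-by-treatment term.
- State the go/no-go criterion that was applied and the number of R33 participants with pre- and post-treatment scans, so that readers can place the result within the range above.

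The cost is some wording and one extra model on data already being collected. The real downside is lower precision for the replication test. On the reading of 0.75 used above, power is about 97% if nearly all planned R33 scans were obtained and 73% at 30 per arm, and it may lie toward the lower end because imaging of new participants ended in 2022.

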### **Phone/Online Screen**

Prospective participants will either 1) contact the study coordinator's office at Duke or be called for a telephone screening interview, administered by the Duke Study Coordinator/approved study team member, or 2) they may visit the websites such as ClinicalTrials.gov, Dukehealth.org, DukeList, Reddit, UNC Psychiatry site, Facebook/IG and see the study description or posting. The telephone-screening instrument (see telephone script) is designed to rule out individuals who clearly meet certain exclusion criteria. The Duke study coordinator or approved study staff member will go through the telephone script document within UNC's REDCap & will be directly entering potential participant's responses to the telephone script electronically--thus no paper copies of the telephone script will exist.

As an aid to shorten the recruitment prescreening process, prospective participants will be directed by all Duke/UNC flyers & brochures, online postings, Facebook/IG ad briefs, emails to UNC listserv & Duke's DEPRU registry, to the REDCap online screen survey within UNC's REDCap platform. Once on the REDCap online screen, they will read a description of the study (a modified version of the IRB approved phone screen) and if interested, will continue with answering the online screen questions (see online screen script for REDCap). The REDCap survey begins with an information statement designed to describe the study, risks and benefits in the absence of informed consent. If they agree to continue, they will then be asked their current age & if their age meets the study inclusion/exclusion criteria, they will continue on with the rest of the REDCap online screen as per REDCap online script. If they do not meet the age requirement, they will receive a message in REDCap indicating that they are not eligible and the survey will end. The results from the REDCap online survey will be monitored by the Duke/UNC study coordinator and other approved Duke/UNC study staff who will have access via a username and password. The data from the online survey can be imported to a SPSS or an excel .csv file which can only be accessed by the approved study team. Each day, study staff can check results of the online survey to see if any new potential participants have completed the survey and contact those people to either set up their first appointment or inform them that they don't qualify for the study per inclusion/exclusion criteria. Upon reviewing the prescreening information from REDCap by the study coordinator or Duke/UNC approved designated study staff, if it is noted that the subject did not complete all of the online screen questions, the plan is for the study coordinator/staff to contact the subject. They would thank them for starting the screen and prompt them to complete the online screen again or by phone (if easier, using the phone script) if they are still possibly interested in the study.

